**Table 3: Outcomes at Six Months in All Subjects**

| Measure                                    | Device+ OMM |                          | OMM |                  | Difference                  |
|--|-------------|--------------------------|-----|------------------|-----------------------------|
|  | N           | Mean±SE                  | N   | Mean±SE          | Mean±SE                     |
| Six-minute hall walk (meters)              | 56          | 59.6 § ± 14.1 | 43  | 1.5 ± 13.2       | 58.1 † ± 19.8    |
| Quality of life (points)                   | 64          | -17.4 § ± 2.8 | 54  | 2.1 ± 3.1        | -19.5 ± 4.2                 |
| New York Heart Class
(% improved)       | 64          | 55% §         | 54  | 24% § | 31% ‡            |
| LVEF (%)                                   | 49          | 2.4 § ± 1.1   | 40  | -0.1 ± 1.3       | 2.5 ± 1.7                   |
| NT-proBNP (pg/ml)*                         | 43          | -69 (-504, 198)          | 40  | 129.5 (67, 619)  | -341.5 ‡ ± 189.8 |
| # of HF Hosps
6M Pre/Post Randomization | 57          | -0.49 § ± 0.2 | 50  | -0.05 ± 0.22     | -0.44 ± 0.29                |

\* Non-parametric analyses

†  $p \leq 0.01$ ; ‡  $p \leq 0.05$

§ Within group  $p \leq 0.05$

The event-free rate of all system- and procedure-related major adverse neurological and cardiovascular events (MANCE) was 97.2% (lower 95% confidence bound 91.4%). A manuscript of the results of these studies was accepted for publication in February 2015 and will be available in March 2015 (JACC HF 2015).

### 1.2.3. Additional Human Clinical Analysis

In addition to the above summary results, subgroup analyses were prospectively defined in the Statistical Analysis Plan for the purposes of hypothesis generation and refinement of future clinical trial designs. An important pre-defined subgroup analysis was performed on subjects who did not have a cardiac resynchronization therapy (CRT) device at baseline. Over 2/3 (68%) of the global randomized heart failure subjects did not have a CRT device at baseline. In this large cohort, the subjects receiving BAT showed a significant improvement from baseline to six months in six-minute hall walk, quality of life measured by the MLWHF, NYHA, and left ventricular ejection fraction, as shown in Table 4. The BAT group also showed a decrease in NT-proBNP at six months. Compared to the OMM arm, the BAT arm experienced clinically relevant and statistically significant improvements in the six-minute hall walk, quality of life, left ventricular ejection fraction, and NT-proBNP. Non-significantly, the percent of subjects who improved in at least one NYHA Class was higher in the BAT arm. Similar to the full study cohort, there is evidence that BAT reduces the number of days spent in a hospital for heart failure six months after commencing therapy compared to six months pre-therapy within

the device arm (reduction of 9 day per patient per year,  $p=0.012$ ) as well as between the two arms (reduction of 9 day per patient per year,  $p=0.057$ ).

**Table 4: Outcomes at Six Months in Subjects with No CRT at Baseline**

| Measure                                   | Device |                          | OMM |                | Difference               |
|---|--------|--------------------------|-----|----------------|--------------------------|
|   | N      | Mean±SE                  | N   | Mean±SE        | Mean±SE                  |
| Six-minute hall walk (meters)             | 35     | 85.5 § ± 20.5 | 30  | 3.6 ± 16.3     | 81.9 ± 26.8              |
| Quality of life (points)                  | 42     | -21.6 § ± 3.6 | 37  | 3.5 ± 3.7      | -25.1 † ± 5.2 |
| New York Heart Class
(% improved)      | 42     | 48% §         | 37  | 27%            | 21%                      |
| LVEF (%)                                  | 32     | 4.3 § ± 1.2   | 27  | -0.1 ± 1.7     | 4.4 ‡ ± 2.0   |
| NT-proBNP (pg/ml)*                        | 29     | -97 (-504, 93)           | 29  | 116 (-74, 700) | 318 ‡ ± 274   |
| HF Hosp Days
6M Pre/Post Randomization | 38     | -8.8 § ± 4.0  | 34  | 0.18 ± 2.2     | -9.07 ± 4.7              |

\* Non-parametric analyses

†  $p \leq 0.01$ ; ‡  $p \leq 0.05$

§ Within group  $p \leq 0.05$

In summary, the cohort of BAT subjects who did not have CRT at baseline showed consistent, and mostly significant, improvement across all efficacy endpoints. This is particularly evident when compared to the OMM only subjects, who demonstrated no improvement and even evidence of deterioration. In addition, the rate of heart failure hospitalization showed improvement in the BAT device arm six months post versus pre-enrollment, which is compared to a trend of no improvement in the OMM only arm.

### 1.3. Conclusions

Through the well-documented abilities of the baroreflex to modulate a host of physiologic properties, BAT targets many of the pathologies associated with HF. As previously demonstrated in patients with resistant hypertension, BAT reduces afterload, consequently reducing filling pressures, and left atrial size. Accompanying these structural changes are chronic reductions in sympathetic nerve activity and plasma norepinephrine, increased parasympathetic nerve activity, and improved heart rate variability. Dilation of arteries and veins promotes skeletal muscle and coronary perfusion, normalizes blood flow distribution, and lowers central venous pressure, a key determinant of clinical outcome. Autonomic and circulatory changes promote preservation of renal function through maintenance of renal blood flow and reduction of central venous pressure. Baroreflex-mediated changes may also ameliorate pulmonary hypertension, a common co-morbidity in HF. Results of clinical studies to date are consistent with results from basic science studies, suggesting that the mechanisms of action observed in animal models are relevant to clinical pathophysiology as well. The pre-specified subgroup analysis on the global

randomized heart failure subjects who do not have CRT present at baseline provides consistent and comprehensive evidence of a clinically relevant and statistically significant benefit of the BAT device in this cohort of patients. Thus, this pivotal study is intended to confirm the positive effects of the BAT device in the patient population which does not currently have and is not currently indicated for a CRT device.

#### 1.4. Recent Information

After evaluating the pre-planned Phase 1 interim data described in previous protocol revisions, a large, important and clinically relevant population emerged. This population is characterized by having NYHA Class III heart failure, left ventricular ejection fraction (LVEF) <35% and baseline core lab NT-proBNP < 1600 pg/ml. To adequately evaluate this population, Revision F will actively enroll only subjects with a baseline core lab NT-proBNP < 1600. As interim data collection for the initial Phase 1 analysis is complete, Revision F will focus on the Phase 2, or morbidity and mortality extended phase, of the study. As such, the total number of subjects previously and prospectively randomized will enable the evaluation of a morbidity and mortality benefit in subjects with a baseline core lab NT-proBNP < 1600 pg/ml.

## 2. PURPOSE

The purpose of this clinical trial is to develop valid scientific evidence for safety and effectiveness of Baroreflex Activation Therapy® with the BAROSTIM NEO System in subjects with heart failure, defined as New York Heart Association (NYHA) functional Class III, left ventricular ejection fraction (LVEF)  $\leq$  35% and NT-proBNP < 1600 pg/ml despite being treated with the appropriate heart failure guideline directed therapy, excluding subjects eligible for or actively receiving Cardiac Resynchronization Therapy (CRT).

The total trial duration is anticipated to be approximately 5 years; however, the duration of an individual subject enrollment will depend on when he or she entered the trial.

## 3. PROTOCOL

### 3.1. Trial Summary

The BAROSTIM NEO - Baroreflex Activation Therapy for Heart Failure is a prospective, randomized trial in subjects with reduced ejection fraction heart failure. Subjects will be randomized in a 1:1 ratio to receive Barostim Activation Therapy with an implanted BAROSTIM NEO System in addition to medical management or to receive medical management alone (no device implant). The trial will be conducted at up to 120 investigational centers in the U.S. and up to 20 investigational centers outside the U.S. These centers will enroll up to 1200 subjects to randomize approximately 480 subjects who meet the entry criteria.

A single center will not be permitted to randomize more than 15% of the total number of randomized subjects. A subject will be considered enrolled when he or she has provided written consent.

Post-consent screening measurements will be obtained only after the subject has completed a medication optimization and 4-week medication stabilization period. For all subjects, the heart failure medication regimen must remain stable during the 4-week medication stabilization period, except for minor adjustments (see inclusion criterion #5 in section 3.3.1). Subjects will be randomized when they have met all enrollment criteria and after all baseline measurements have been obtained.

Prior to randomization, site personnel will be required to provide an anticipated implant date. For subjects randomized to the Medical Management Arm, this date will be used for the timing of all other trial visits. For subjects randomized to the Device Arm, trial visits will be based on the actual date of device implant.

Device subjects will have the device activated prior to being discharged from the hospital, and should remain at the hospital for at least 2 hours post-programming for observation prior to being discharged. At the physician's discretion subjects may remain overnight for observation to evaluate programming.

For all subjects, trial visits will occur at 0.5, 1, 1.5, 2, 3, 6, 9 and 12 months post-implant (post anticipated implant for medical management). Visits will occur quarterly from 15 to 24 months and semi-annually thereafter.

Subjects are followed in an identical manner regardless of trial arm.

Figure 7 provides a schematic of the overall trial design.

**Figure 7: Trial Schematic**

For US study subjects only: Once the device is commercially approved by the FDA and the study has ended, CVRx may provide one BAROSTIM NEO device at no charge for each subject in the Medical Management arm that was active when the study ended; refer to the IRB approved informed consent language. CVRx has not agreed to cover any of the other costs related to implantation of the device. Subjects or their healthcare insurer must arrange for payment of all other costs such as pre-surgical physical, hospital costs, surgeon and anesthesia fees. Other conditions, as described in the consent form, must also be met.

### 3.2. Trial Data

All randomized subjects will complete the prescribed protocol follow-up as detailed in Table 5 Time and Events Schedule. The six month data will provide evidence of the safety and efficacy of Barostim Therapy. The accumulated morbidity and mortality

data collected will provide evidence of morbidity and mortality benefit. This trial will involve one or more interim analyses to evaluate when sufficient evidence is reached for the final morbidity and mortality analysis. Up to 1,200 subjects may be enrolled to reach the anticipated sample size of 480 randomized.

### 3.3. Eligibility Criteria

#### 3.3.1. Inclusion Criteria

To be eligible for this trial, subjects must meet all of the following inclusion criteria:

1. Age 21 years or above.
2. Currently NYHA Class II or III heart failure. For NYHA Class II, must have been NYHA Class III at any point in time within 3 calendar months prior to enrollment or at time of screening (enrollment is defined as the date the subject provided written consent).
3. Left ventricular ejection fraction  $\leq$  35% within 45 days prior to randomization.
4. Heart failure accompanied by either:
  - Core lab NT-proBNP  $\geq$  400 AND  $<$ 1600 pg/ml within 45 days prior to randomization **OR**
  - Core lab NT-proBNP  $<$  400 pg/ml within 45 days prior to randomization AND a heart failure hospitalization in the past 12 months.

**Note:** Heart failure hospitalization may include an overnight hospital or hospital-based observation unit stay with a primary diagnosis of heart failure or an emergency room visit with a primary diagnosis of heart failure.

**Note:** Screening/Baseline core lab NT-proBNP must be collected in an outpatient setting at a time when the subject is thought to be clinically stable.

5. On optimal, stable, Guideline Directed Medical Therapy (GDMT) per country specific guidelines for the treatment of heart-failure throughout screening/baseline evaluation and for at least 4 weeks prior to obtaining any post-consent screening parameters:
  - No more than a 100% increase or a 50% decrease of the dosage of any one medication other than a diuretic.
  - Medication changes within a drug class are allowed as long as the equivalent dosage is within the limits specified above.
  - Unrestricted changes in diuretics are allowed as long as the subject remains on a diuretic.
6. Six-minute hall walk (6MHW)  $\geq$  150 m AND  $\leq$  400 m within 45 days prior to randomization.

7. The artery planned for the BAROSTIM implant must meet both of the following criteria:
  - At least one carotid bifurcation as identification by a bilateral carotid duplex ultrasound within 6 months prior to randomization that is:
    - a. Below the level of the mandible AND
    - b. No ulcerative carotid arterial plaques AND
    - c. No carotid atherosclerosis producing a 50% or greater reduction in linear diameter in the internal carotid AND
    - d. No carotid atherosclerosis producing a 50% or greater reduction in linear diameter in the distal common carotid
  - No prior surgery, radiation, or endovascular stent placement in the carotid artery or the carotid sinus region.
8. If female and of childbearing potential, must use a medically accepted method of birth control (e.g., barrier method with spermicide, oral contraceptive, or abstinence) and agree to continue use of this method for the duration of the trial. Women of childbearing potential must have a negative pregnancy test within 14 days prior to randomization.
9. Received a standard cardiac work up and is an appropriate candidate for the study and the surgical procedure as determined by a trial cardiologist and a trial surgeon.
10. Subjects implanted with a cardiac rhythm management device that does not utilize an intracardiac lead, or implanted with a neurostimulation device, must be approved by the CVRx Clinical department.
11. Signed a CVRx-approved informed consent form for participation in this trial.

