**Table 5: Time and Events Schedule**

| Procedure                        |        |    |         |                            | Months from Implant |   |     |   |   |   |   |    |        |             |
|----------------------------------|--------|----|---------|----------------------------|---------------------|---|-----|---|---|---|---|----|--------|-------------|
|                                  | Screen | BL | Implant | Activate/
Pre-discharge | .50                 | 1 | 1.5 | 2 | 3 | 6 | 9 | 12 | 15-24* | After 24*** |
| Subject Informed Consent         | X      |    |         |                            |                     |   |     |   |   |   |   |    |        |             |
| Assess Enrollment Criteria       | X      |    |         |                            |                     |   |     |   |   |   |   |    |        |             |
| Demographics/Medical History     | X      |    |         |                            |                     |   |     |   |   |   |   |    |        |             |
| Physical Assessment              | X      | X  |         |                            | X                   | X | X   | X | X | X | X | X  | X      | X           |
| Subject Medications              | X      | X  |         |                            | X                   | X | X   | X | X | X | X | X  | X      | X           |
| Adverse Events                   | X      | X  | X       | X                          | X                   | X | X   | X | X | X | X | X  | X      | X           |
| LVEF                             | X      |    |         |                            |                     |   |     |   |   |   |   |    |        |             |
| Six Minute Hall Walk             | X      | X  |         |                            |                     |   |     |   |   | X |   | X  |        |             |
| Core lab NT-proBNP               |        | X  |         |                            |                     |   |     |   |   | X |   | X  |        |             |
| eGFR                             | X      |    |         |                            |                     |   |     |   |   |   |   |    |        |             |
| Carotid Duplex Ultrasound†       | X      |    |         |                            |                     |   |     |   |   |   |   |    |        |             |

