#### **3.4.8.3. Screening Six Minute Hall Walk Test (6MHW)**

The 6MHW is required at screening and must occur within 45 days prior to randomization to confirm that the distance walked is  $\geq 150$  m AND  $\leq 400$  m. Subjects who do not complete the test are excluded from the trial. Instructions for performing the 6MHW are provided in Appendix 2 Six Minute Hall Walk Test. These instructions include the definition of a complete hall walk, and a clear and well-defined script that provides site personnel with exact verbiage to use with the subjects during the test. The length of the corridor should be marked every 3 meters to provide an easy way to accurately measure the distance walked.

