### **3.4.9. Baseline Visit**

For each assessment that occurs for both Screening and Baseline (e.g. Physical Assessment, Subject Medications, Adverse Event, Six Minute Hall Walk and NYHA Class Assessment), the Screening and Baseline assessments must be completed on separate days. For example, the Screening and Baseline six-minute hall walk must not be done on the same day.

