**3.4.9.2. Baseline Six Minute Hall Walk Test (6MHW)**

A 6MHW will be performed at baseline. It is very important that each subject attempts to complete the 6MHW assessment. The reasons for inability to do the test, or for stopping the test early, will be collected.

Instructions for performing the 6MHW are provided in Appendix 2 Six Minute Hall Walk Test. These instructions include a clear and well-defined script that provides site personnel with exact verbiage to use with the subject during the test. The length of the corridor should be marked every 3 meters to provide an easy way to accurately measure the distance walked.

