#### **3.4.10. Randomization**

Once the subject has been determined to meet all eligibility criteria and all baseline measurements have been obtained, subjects may be randomized. Subjects will be randomized 1:1 to either medical management or device and medical management. The randomization assignment will be stratified by site and obtained via the electronic data capture (eDC) system.

Prior to obtaining the randomization assignment, an intended device implant date must be entered into the eDC system. This will be used as the date for the timing of follow-up visits for those randomized to the medical management arm. The actual implant date will be used as the date for the timing of follow-up visits for those randomized to the device arm.

Details on the Implant Procedure Testing and Data for subjects randomized to device may be found in Section 3.4.12 Implant Procedure Testing and Data.

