### 3.2.4. Long Term Sustainable Improvement

#### Six Minute Hall Walk (6MHW)

The mean improvement in 6MHW between baseline and 12 months by treatment arm will be presented with means and confidence intervals using a regression model of change from baseline with covariates for randomized group and baseline value. A generalized estimating equation (GEE) repeated measures model with a compound symmetry working correlation will be used to account for within subject correlation over time and to estimate the difference between the randomized arms over all times at which the endpoint is collected, adjusted for baseline.

**Rationale:** Improving symptoms is important to patients, particularly an improvement in exercise capacity (6MHW). Previously, a clinically and statistically significant symptomatic improvement was established at six months for 6MHW. This endpoint will evaluate the long term, sustainability of an improvement in 6MHW between the treatment arms.

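### The 12-month six-minute walk models could also adjust for the screening walk: a small, free gain in precision, not an error

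*Protocol*

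**What the plan says.** **Two walks before randomisation.** Inclusion criterion 6 (Protocol 3.3.1) asks for a walk of at least 150 m and at most "400 m within 45 days prior to randomization". Protocol 3.4.8.3 states: "The 6MHW is required at screening and must occur within 45 days prior to randomization". Protocol 3.4.9.2 adds: "A 6MHW will be performed at baseline". The Table 5 row "Six Minute Hall Walk" marks both visits, then months 6 and 12. Section 3.4.9 keeps the two apart: "the Screening and Baseline six-minute hall walk must not be done on the same day". Section 3.4.10 places both ahead of allocation, since only once eligibility is met and "all baseline measurements have been obtained, subjects may be randomized". Neither value can therefore be affected by treatment.

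**Completeness of the screening walk.** Section 3.4.8.3 says: "Subjects who do not complete the test are excluded from the trial". Under the current text a complete screening distance exists for everyone randomised.

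**The analysis.** The 12-month walk is one of the focused endpoints in SAP 3.2.4. It is analysed with a "regression model of change from baseline with covariates for randomized group and baseline value". The accompanying repeated-measures GEE is likewise adjusted for baseline. Neither supplied document uses the screening distance as a covariate or averages it into the baseline. SAP 3.2 gives the focused endpoints nominal two-sided 95% intervals and p-values, and says they are meant to support labeling.

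**The concern.** A single walk measures a subject's walking capacity with day-to-day noise. A second walk on another day, also before randomisation, carries further information on that capacity. Used as a second covariate it lowers the expected residual variance of the treatment comparison. It cannot bias the comparison, because it precedes allocation. Sites and patients have already borne the cost of the measurement.

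What is at stake is the width of one interval on an endpoint intended for labeling. SAP section 7 says COVID-19 reduced or delayed walk testing at follow-up visits, so the number of 12-month walks is probably below the 319 in the analysis population, and cheap precision is worth having.

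**Working it through.** **1. Variance figures in the documents.** Protocol Tables 3 and 4 give six-month walk changes as mean ± SE. With SD = SE × √n, and pooled SE = pooled SD × √(1/n₁ + 1/n₂):

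| Source | Device SD | Control SD | Pooled SD | SE of difference | Stated |
|---|---|---|---|---|---|
| Table 3, all subjects | 14.1 × √56 = 105.5 m | 13.2 × √43 = 86.6 m | 97.8 m | 97.8 × √(1/56 + 1/43) = 19.8 m | 19.8 m |
| Table 4, no CRT at baseline | 20.5 × √35 = 121.3 m | 16.3 × √30 = 89.3 m | 107.7 m | 107.7 × √(1/35 + 1/30) = 26.8 m | 26.8 m |

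Both stated SEs reproduce. Table 4 is the closer population, because this trial excludes subjects receiving CRT.

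**2. Model.** Let T be true capacity (SD σ_T). The screening walk is S = T + e₁ and the baseline walk is B = T + e₂. The 12-month walk is Y = T + d + e₃, where d is true change. Each e has SD σ_e. The SD of Y − B is set to the documents' figure. σ_T and σ_e are not in the documents and are assumptions.

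**3. One case by hand, ignoring the eligibility window.** Take σ_T = 80 m, σ_e = 30 m and SD of change 97.8 m.

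- Var(d) + σ_e² = 97.8² − 30² = 9,565 − 900 = 8,665.
- Given B alone: Var(T|B) = 6,400 × 900 / 7,300 = 789, so the residual variance is 8,665 + 789 = 9,454.
- Given B and S: Var(T|B,S) = 6,400 × 450 / 6,850 = 420, so the residual variance is 8,665 + 420 = 9,085.
- Reduction: (9,454 − 9,085) / 9,454 = 3.9%. Interval width falls by 1 − √(9,085 / 9,454) = 2.0%.

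**4. With the eligibility window.** Restricting S to 150–400 m narrows its spread and lowers its added value; the case above drops from 3.9% to about 3.2%. Simulated over σ_T of 70–90 m and σ_e of 20–40 m, with assumed mean capacity 290 m:

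| SD of change | Cut in residual variance | Cut in interval width |
|---|---|---|
| 98 m (Table 3) | 1.7–4.7% | 0.9–2.4% |
| 108 m (Table 4) | 1.4–3.9% | 0.7–2.0% |

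**5. In subjects and metres.** A variance cut v is worth N × (1/(1 − v) − 1) subjects. With N = 319, v = 1.4% gives 319 × 0.0142 ≈ 5 and v = 4.7% gives 319 × 0.0493 ≈ 16.

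The 95% half-width, using the SD of change as an upper approximation to the residual SD, is:

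- 1.96 × 97.8 × √(4/319) = 21.5 m, falling by 0.9–2.4%, or 0.2–0.5 m.
- 1.96 × 107.7 × √(4/319) = 23.6 m, falling by 0.7–2.0%, or 0.2–0.5 m.

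These figures are for the 12-month regression. The GEE was not simulated separately.

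**The case against.** The strongest reply is that nothing here is wrong. Adjusting for one baseline value is a standard, valid analysis. The 12-month walk has no stated power, sample size or success threshold, and no decision in the plan turns on half a metre. All of that stands, and it is why the point is only a suggestion.

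The stated purpose of SAP 3.2.4 is to see whether the six-month effect persists, so consistency with the earlier six-month model could justify the present covariates. That model would be in the main SAP (360050-001), which was not supplied. This part stands as a reason to check, but the supplied text does not give it as a rationale.

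Two stronger readings are tempting and are not supported:

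- **That subjects with a missing baseline walk drop out of the model although a screening walk exists.** Protocol 3.1 and 3.4.10 require baseline measurements before randomisation. Appendix 2 has staff record the distance of a walk stopped early, so such a walk is not a missing value. Section 3.4.9.2 does allow for inability to do the test, but by plan this should be rare. Substituting the screening walk would also conflict with keeping change defined from the Baseline visit.
- **That the gain reaches 7% of variance or about 22 subjects.** Under these assumptions that needs an SD of change below the pooled 98 m and 108 m in the protocol's own tables.

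**Conclusion.** The point holds as a small, free improvement in precision. The plan collects two pre-randomisation walks and adjusts for one. Using both would cut residual variance by about 1.4–4.7% and interval width by about 0.7–2.4%, worth roughly 5–16 subjects out of 319. The true figure will be lower in subjects because 319 is the morbidity and mortality population, not the number with a 12-month walk.

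A reader might infer that the planned comparison is biased or inadequate. It is neither.

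The size rests on assumed test-retest noise, capacity spread and mean capacity, and on six-month SDs from earlier studies standing in for 12-month SDs in this trial. The direction does not depend on those values, provided the two walks are imperfectly correlated.

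Two facts remain to be confirmed:

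- Whether the main SAP defines the baseline value in some other way. The protocol's Screening and Baseline labels support reading it as the Baseline-visit walk.
- Whether both walks exist for the 259 subgroup subjects already randomised when the further 72 were planned. The visit schedules in earlier protocol revisions were not supplied.

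**What to change.** In SAP 3.2.4 (6MHW), add the screening walk distance as a second pre-randomisation covariate in both the 12-month regression and the GEE. Keep change defined as the 12-month walk minus the Baseline-visit walk. Do not add a rule that substitutes the screening walk for the baseline one.

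Make the change before unblinding. Check first that the main SAP does not already define the baseline value from both walks, and that screening distances are in the database for subjects randomised under earlier revisions. If consistency with the six-month analysis matters, report the single-covariate model beside it.

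The cost is one covariate in the SAP text and the program. It needs no new data, visits or patient burden, and no stated sample size or power figure changes.
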